For the first part of the study, where full AUC analysis will be performed to verify the dose, we anticipate initially enrolling 12 patients to achieve 12 dose verifications. Any patients who do not achieve a complete PK data profile (i.e. due to suboptimal dose or incomplete course of study drug) will be replaced to achieve 12 dose verifications. The total number of patients will still remain 65 (Phase I and Phase II). The age of enrollment for these patients will be limited to 2-12 years old. This age restriction has been imposed because adult dosing for maraviroc in the stem cell transplant setting has already been established and it is likely that teenagers metabolize the drug similar to adults. The second part of the study, where full AUC analysis will not be conducted, will enroll the remaining patients between the ages 2-40 years.

We will enroll eligible patients and maraviroc will be administered as per study rules. Area under the concentration-time curve (AUC) determination will be performed on days 0 +/- 3 days and 10 +/- 3 days to account for weekends, national holidays or clinical deterioration not allowing for scheduled blood draws on the specified days. PK analysis will be performed after the first 3 patients. As per our study design graph, this is not an "interim" analysis, but an analysis to verify PK target attainment which then will drive either further observation or dose escalation. See Figure 1.

[figure not shown]

Figure 1. Study design

Pharmacokinetic measurement and analysis-

Blood for PK will be collected on day 0 +/- 3 days and Day 10 +/- 3 days. Complete PK profile (full AUC) will be performed on these days (see time points below). Evaluation of maraviroc trough levels will also be done routinely on all patients on study on days 0,7,14 and 21 in order to collect additional PK data, verify compliance and allow for additional dose corrections if necessary.

Target AUC/12 hours= $\geq 100\text{ng/mL}$ (based on HIV data)

PK processing will be performed at University of North Carolina's Clinical Pharmacology and Analytical Chemistry Laboratory using mass spectrometer with HPLC separation.

Plasma Maraviroc concentration data will be analyzed by compartmental and non-compartmental analysis with the help of [name], Director of Pediatric Pharmacology Research Unit (PPRU) at CCHMC, and parameter estimates generated will include clearance, half-lives, and volume of distribution along with area under the curve (AUC).

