While data on Maraviroc blood levels are available from other studies, our patients are different from those previously studied, and these first cases will be of great value in determining the levels of drug we can achieve in this population

The time points of obtaining drug levels will be as follows:

- Hour 0- Pre maraviroc administration
- Hour 1 \pm 10 minutes - After maraviroc administration
- Hour 2 \pm 10 minutes- After maraviroc administration
- Hour 4 \pm 10 minutes- After maraviroc administration
- Hour 6 \pm 10 minutes- After Maraviroc administration
- Hour 8 \pm 10 minutes- After maraviroc administration
- Hour 12 \pm 20 minutes- After Maraviroc administration

Plasma concentration-time data will be explored graphically and the AUC will be estimated by non-compartmental analysis with the software package WinNonlin (Version 6.2, Pharsight Corporation, Palo Alto, CA). Full maraviroc PK profile and trough concentration data will be analyzed using a PK model-based Bayesian approach (MW/Pharm, MediWare, Groningen, the Netherlands).

Pharmacodynamic analysis will be performed in the laboratory using standard techniques.

Pharmacodynamic assessments will occur on days 0 +/-3 days and one time on day 14 +/- 3 days after stem cell infusion. Results will be available in a timely fashion to correlate with pharmacokinetic test results.

Dose escalation criteria-

Dose escalation will take place if all the requirements listed below are met:

1. The AUC/12 hours of the initial 2/3 patients is below 100 ng/ml

2. No more than 0 of 3 or 1/6 patients on the first dose level experience a dose limiting toxicity by day 30, defined as either-
 - a. Non-engraftment by day 30. Engraftment is defined as the first of three consecutive measurements of ANC>500/mcL over 3 or more days.
 - b. Grade 4 liver abnormalities, unless clearly related to stem cell transplant and not to the study drug, including but not limited to grade 4-5 liver toxicity due to hepatic veno-occlusive disease, grade 4-5 organ toxicities related to expected infections following stem cell transplant and their sequelae, or grade 4-5 toxicities related to graft versus host disease.

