 - c. Other grade 4-5 toxicity , unless clearly related to stem cell transplant and not to study drug, including but not limited to veno-occlusive disease of the liver, acute graft versus host disease, autoimmune cytopenias, infectious complications due to stem cell transplant, or organ toxicities due to conditioning regimens.

BSA	Original Dose	Dose escalation	Value increment/dose
<0.22	40 mg bid	50 mg bid	+ 10 mg
0.2-0.43	100 mg bid	120mg bid	+ 20 mg
0.44-0.72	200 mg bid	250 mg bid	+ 50 mg
0.73-1.19	300 mg bid	350 mg bid	+ 50 mg
1.20-1.30	300 mg bid	350 mg bid	+ 50 mg
1.31-1.73	300mg bid	350 mg bid	+ 50 mg
>1.73	300 mg bid	350 mg bid	+ 50 mg

Table 4. Table showing doses and increments for dose escalation of Maraviroc.

Stopping Rules

1. If the incidence of Grade 2-4 acute GI or Liver (visceral) graft versus host disease is greater than 50% in the first 20 subjects by day +100, the study will be stopped. Enrollment will not stop while the analysis is being conducted.

2. If 3 out of 6 subjects experience DLT by day +30 as defined above at the initial dose in the first phase (AUC analysis) of the study, the study will be stopped. Enrollment will not be suspended while the analysis is being conducted.
3. The study will be halted for any grade 4 liver toxicity occurring within 30 days of study drug administration and without clear attributable alternative cause. Enrollment will be suspended while an analysis of the toxicity is being conducted. Enrollment will only restart with approval of the Medical Monitor, IRB and FDA. (Of note: any grade 3 liver toxicity (ALT > 5xULN or Total Bilirubin > 3xULN), regardless of cause, will lead to permanent discontinuation of Maraviroc for that specific patient, but enrollment will continue.)

Primary study end points

1. Feasibility
2. GVHD incidence by day +100 (all grades)
3. pK target >100ng/ml

Secondary Study end points

1. Overall survival by day +100
2. Graft failure by day + 100
3. Primary disease relapse by day +100
4. Incidence of toxicities either due to drug or transplant
5. Infectious complications which include asymptomatic viremias for EBV, Adenovirus, CMV, and/or viral disease, bacterial and fungal infections as documented by blood cultures.
6. Time to neutrophil and platelet engraftment

GVHD will be graded according to IBMTR criteria as shown in table 5 [33]-

	Stage 0	Stage 1	Stage 2	Stage 3	Stage 4

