Study calendar for blood draws for patients undergoing formal AUC analysis-

Days	AUC	Trough drug level	Pharmacodynamic assessment
Pretransplant			x
Day 0	X (± 3 days)		X (± 3 days)
Day 7		x (± 2 days)	
Day 10	X (± 3 days)		
Day 14		x (± 3 days)	X (± 3 days)
Day 21		x (± 3 days)	

Table 6. Study calendar for blood draws for patients undergoing formal AUC analysis

For patients enrolled after maraviroc dose has been verified, the schedule for lab draws is shown on Table 7.

Days	Trough drug level	Pharmacodynamic assessment
Pretransplant		x
Day 0	x (± 3 days)	X (± 3 days)
Day 7	x (± 2 days)	
Day 14	x (± 3 days)	X (± 3 days)
Day 21	x (± 3 days)	

Table 7- Study calendar for blood draws for patients on second phase of study (after PK study complete and dose verified)

Volume of Blood Draws-

For pharmacokinetic analysis, we will need approximately 3 ml of blood, to be collected in an EDTA tube. Real time data results will be available to allow for dosing changes to

be made after the first 3 patients. For pharmacodynamics analysis, we will need 2 ml blood in a sodium heparin tube.

Discontinuation of therapy-

Since most patients experience severe toxicities while undergoing an allogeneic SCT, it will be the investigator's responsibility to determine whether certain adverse events are related to the study drug or not based on previous studies using the agent and the current labeling. Common Terminology Criteria for Adverse Events (CTCAE) version 4.0 will be used to report toxicities.

The following events will mandate stopping Maraviroc for a specific patient;

- Grade 3 liver toxicity (ALT > 5xULN or Total Bilirubin > 3xULN) regardless of cause

Maraviroc will not be restarted in these cases.

The following events will mandate holding Maraviroc therapy on a specific patient:

1. Grade 3 or higher toxicity (exclusive of liver toxicity, see section above), not attributable to underlying disease.
2. Infection, which requires treatment with a strong CYP450 inducer or inhibitor (predicted to adversely interact with Maraviroc) such as rifampin.
3. Drop in renal function to creatinine clearance <40 ml/min as measured by GFR or cystatin C.

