The drug can be restarted at the same dose after full recovery from the AEs. Maraviroc will be discontinued if the AE recurs after re-challenge. Any grade 3 liver toxicity (ALT > 5xULN or Total Bilirubin > 3xULN) regardless of cause will lead to permanent discontinuation of Maraviroc for that patient. The study will be halted for any grade 4 liver toxicity occurring within 30 days of study drug administration without clear attributable alternative cause (see stopping rules for details). Re-challenge is not permissible in the event of Grade 3 or higher liver toxicity (ALT > 5xULN or Total Bilirubin > 3xULN) regardless of cause. Any grade 1 or 2 toxicities related to study drug will not require study drug to be held.

Early termination of study drug-

Treatment will continue unless one of the following criteria applies:

1. A dose limiting toxicity (DLT) occurs. A DLT is defined as either-
 - a.) Non-engraftment by day 30, if assessed by the investigator to be related to the study drug. Engraftment is defined as the first of three consecutive measurements of ANC>500/mcL over 3 or more days.
 - b.) Grade 4 liver abnormalities, once other causes for liver toxicity have been ruled out.
 - c.) Other grade 4-5 toxicity determined by the investigator to be related with high probability to the study drug.
2. Any grade 3 or higher liver toxicity (ALT> 5xULN or Total Bilirubin > 3xULN) regardless of cause:
 - a. Any grade 3 liver toxicity (as defined above) will lead to permanent discontinuation of Maraviroc for that patient.
 - b. The study will be halted for any grade 4 liver toxicity occurring within 30 days of study drug administration without clear attributable alternative cause. (See stopping rules for specific details.)
3. Patient decides to withdraw from the study due to inability to take the drug.
4. Poor compliance to drug (missing either 6 consecutive doses (3 days) or 12 intermittent doses in the entire administration period (< 80% compliance)).

Patients removed from study for unacceptable adverse events will be followed until the adverse event resolves or stabilizes.

Toxicity Monitoring-

Maraviroc is generally well tolerated in children as noted in the phase 1 congenital HIV trial. However, a black box warning for hepatotoxicity exists. Therefore, liver function tests will be monitored on patients while on maraviroc every 48 hours until day+30 (+ 7 days).

General concomitant medication and supportive care guidelines

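### Trough-driven dose raises carry no DLT condition or cap, and read literally, a first-phase DLT on a raised dose does not count toward the 3-of-6 stop

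*Combined protocol and SAP*

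**What the plan says.** **Individual corrections.** Under Pharmacokinetic measurement and analysis: "Evaluation of maraviroc trough levels will also be done routinely on all patients on study on days 0,7,14 and 21". One stated purpose is to "verify compliance and allow for additional dose corrections if necessary". The section gives no trigger level, direction, step, ceiling or toxicity condition. Its target is an AUC over 12 hours of at least 100 ng/mL. There is no upper exposure limit and no trough target.

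**Cohort escalation.** Under Dose escalation criteria: "Dose escalation will take place if all the requirements listed below are met". The first requirement is an AUC over 12 hours below 100 ng/mL in 2 of the first 3 patients. The second is "No more than 0 of 3 or 1/6 patients on the first dose level experience a dose limiting toxicity by day 30". Table 4 gives one escalated dose per body-surface-area band, 10 to 50 mg per dose above Table 1.

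**Trial-level DLT stop.** Stopping Rules, item 2: "If 3 out of 6 subjects experience DLT by day +30 as defined above at the initial dose", in the first (AUC) phase, the study stops. Enrollment continues during the analysis.

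**Protections that do not depend on dose.** Stopping rule 3 halts the study for grade 4 liver toxicity with no clear other explanation. Discontinuation of therapy requires drug to be stopped for grade 3 liver toxicity and held for other toxicity of grade 3 or above unless the underlying disease explains it. Early termination of study drug ends treatment for a child with a DLT. The Data Safety Monitoring Plan has a medical monitor review unexpected serious events and deaths and advise on continuation.

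**The concern.** The escalation criteria do not accept low exposure alone as grounds for a higher dose; the DLT count must also be acceptable. The trough provision offers a second route to a higher dose, child by child, and no sentence ties it to that count. Because the target is only a floor, a low reading points to an increase.

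Rule 2 then adds a counting problem. It is worded for the initial dose, and the plan does not say where to count a child whose dose changed part-way. The same gap covers children on the cohort-escalated dose: no stated DLT count stops the trial for them.

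The first-phase patients are children aged 2-12, and under Toxicity Monitoring the protocol notes that "a black box warning for hepatotoxicity exists". Unexplained grade 4 liver toxicity is covered by rule 3 at any dose. What is at stake is trial-level control, by a stated count, of the other DLTs: non-engraftment by day 30 and non-liver grade 4-5 toxicity.

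**Working it through.** The plan states no operating characteristics for these rules, so there is no figure to reproduce.

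**Step 1: the two thresholds together.** Inputs: Dose escalation criteria, item 2; Stopping Rules, item 2.

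| DLTs in six | Escalation, DLT part | Rule 2 |
|---|---|---|
| 0-1 | met | no stop |
| 2 | barred | no stop |
| 3 or more | barred | stop |

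Exactly 2/6 is the state in which a higher dose is barred for the cohort while the trial continues. The trough provision has no matching bar.

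**Step 2: how often the count lands there.** Assume independent children with DLT rate p, and q = 1 - p. The documents give no rate, so p is varied. A result of 0/3 already meets the DLT condition, so the barred state needs two DLTs in six with at least one among the first three. Of the 15 possible pairs of children, 3 lie wholly within patients 4-6, leaving 12:

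P = 15p²q⁴ - q³ × 3p²q = 12p²q⁴

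| p | 12p²q⁴ |
|---|---|
| 0.05 | 12 × 0.0025 × 0.8145 = 0.024 |
| 0.10 | 12 × 0.01 × 0.6561 = 0.079 |
| 0.20 | 12 × 0.04 × 0.4096 = 0.197 |
| 0.30 | 12 × 0.09 × 0.2401 = 0.259 |
| 0.40 | 12 × 0.16 × 0.1296 = 0.249 |
| 0.50 | 12 × 0.25 × 0.0625 = 0.188 |

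The maximum, at p = 1/3, is 12 × (1/9) × (16/81) = 0.263. The range is therefore about 2% to 26%. This is the chance of the DLT count only. It is not the chance that a child is raised or that a DLT goes uncounted.

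**Step 3: how a raised child is counted.** Suppose three of six first-phase children have a DLT, one of them on a raised dose.

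| Reading | Count | Rule 2 |
|---|---|---|
| By assigned starting level | 3/6 | stop |
| Raised child leaves the count entirely | 2/5 | no stop yet; a sixth child is needed |

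The text does not choose between these. The second follows the literal words of rule 2, and under it the raised child's DLT never enters.

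**Step 4: timing.** The last trough is on day 21 (±3 days) and the DLT reading is on day 30. Corrections can therefore precede the evidence the escalation rule relies on. Non-engraftment by day 30 is known only after all four troughs, so in a raised child it always follows the raise.

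**The case against.** The strongest reply is that no bypass is written down. The trough sentence states a purpose of sampling; it names no direction and does not authorize a dose above Table 1. The protocol elsewhere says drug is given under the study rules, and the escalation criteria are its only stated rule for a higher dose, so corrections may be meant to fall under them. The Volume of Blood Draws section says "Real time data results will be available to allow for dosing changes to" follow once three patients are in, which can be read as the cohort decision alone. Figure 1, which carries the decision path, is not shown. The words initial dose can also mean the assigned level, and counted that way no DLT is lost.

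All of this stands as a possible reading. It does not close the gap. The corrections are called additional, and they extend to the second part, where no full AUC is taken and the escalation rule's AUC requirement cannot be applied.

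Three stronger readings are tempting, and the documents do not support them.

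- **That the rules expressly conflict.** They do not; one is silent where the other is specific.
- **That a true 3/6 would be read as 2/6.** On that basis, at an assumed 40% DLT rate, the chance of stopping would fall from 46% (3 or more of 6) to 32% (of 5) or 18% (of 4) with one or two raised children. This keeps a raised child among the six while dropping that child's event, which no text says. If the child leaves the count, later children can complete the six, since the first part seeks 12 verifications.
- **That the 12 dose verifications are invalid.** Patients with incomplete profiles "due to suboptimal dose or incomplete course of study drug) will be replaced to achieve 12 dose verifications". Whether a corrected child falls under that clause depends on how suboptimal dose is read, and the day 0 profile would normally still be on the assigned dose.

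Rule 2 covers the first phase only, so second-part DLTs fall outside it at any dose.

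**Conclusion.** The point holds as a gap in wording with a safety consequence. Individual raises have no stated DLT condition or cap. On a literal reading, a first-phase DLT on a raised dose, whether reached by correction or by cohort escalation, does not count toward the 3/6 stop. Investigators following the text faithfully could reach different stopping decisions on the same six children.

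The size is unknown. It depends on the DLT rate and on how many children are raised, and the documents give neither. The 2-26% for the barred-but-running state rests on assumed DLT rates of 5-50% and independence between children. At the low end, which is plausible because the DLT definition excludes grade 4-5 toxicity clearly due to transplant, the state is uncommon. The dose-independent protections limit the harm to any one child and cover unexplained grade 4 liver toxicity at trial level. They do not supply a stated count for the other DLTs.

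**What to change.** 1. **Counting.** Reword rule 2 and the DLT item of the escalation criteria so that every first-phase child's DLT counts, whatever dose was being taken, under the dose level assigned at the start. Apply rule 2's limit to the escalated level as well. Also tabulate DLTs by dose taken.
2. **Cap and bar.** Limit any individual upward correction to the Table 4 escalated dose. Allow none above the Table 1 dose once 2 or more of the first 6 children have had a DLT.
3. **Reporting.** Report target attainment on the assigned dose for all children who started, including those replaced.

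Making every individual correction wait for the day 30 cohort count is not proposed. A child's own dosing ends on day 30, so that would be a debatable trade-off.

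The cost is a few sentences and no new data collection. A few children with low exposure would stay at the Table 1 dose, and the trial could stop for toxicity that arose on a raised dose. The table by dose taken would let the medical monitor see when that is so.

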Maraviroc is not known to significantly affect any metabolic pathway. However, inhibitors and inducers of the cytochrome P450 metabolic pathway affect its drug level. Generally, patients in this trial will receive prophylactic antifungals as directed by their attending physician, which may include either micafungin or ambisome. Other concomitant medications are allowed except for strong inducers or inhibitors of the cytochrome P450, such as voriconazole, phenytoin, carbamazepine and rifampin. (See table 2).

Should there be emesis within 30 minutes of taking maraviroc, the drug should be re – administered. However, any emesis after 30 minutes of taking maraviroc will not require the drug to be readministered.

Risk to unborn fetus-

It is recommended that patients on study utilize appropriate methods of contraception to prevent getting pregnant or fathering a child as the effects of maraviroc on the unborn fetus is unknown. All female patients routinely undergo a pregnancy test as part of pre bone marrow transplant evaluation and only proceed with transplant when it is confirmed that they are not pregnant. Therefore we will not repeat this test prior to starting maraviroc.

Risk associated with blood draws-

This study will require research blood to be drawn as specified time points as shown in the study calendar. This blood will be drawn from a central line whenever possible and will be combined with routine clinical blood draws whenever possible and will not exceed maximum allowed blood volume for that patient per day per standard of care.

Statistical analysis

The primary objectives of this phase I/II clinical trial are to establish a therapeutic dose of Maraviroc and test the 100 day incidence rate of any GVHD in pediatric patients undergoing allogeneic stem cell transplantation against a historical incidence rate.

Phase I will consist of the determination of a therapeutic dose. A dose escalation procedure outlined in the study design will be conducted until a dose which yields 2 of 3 patients with AUC > 100ng/ml and no drug related toxicities.

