Verification of eligibility will be performed and appropriate documentation of informed consent will be documented for all subjects enrolled into the study. The timeliness of Adverse Event and Serious Adverse Event reporting will be monitored to ensure regulatory compliance. All case report forms (CRF) for the first subject enrolled into the study will be monitored for completeness and quality by comparing data in the case report forms to data in the source documents. Thereafter, a minimum of 10% of enrolled subjects' CRFs will be monitored for completeness and quality by comparing data in the case report forms to data in the source documents.

Data Safety Monitoring Plan

A qualified physician not associated with this particular protocol will be chosen as medical monitor for this study. The medical monitor will meet with the PI or designee and review study data/progress a minimum of every 6 months; more often at the discretion of the PI and/or medical monitor.

The medical monitor is required to review all unanticipated problems involving risk to subjects or others, unanticipated serious adverse events and all subject deaths associated with the protocol and provide an unbiased written report of the review.

At a minimum, the medical monitor should comment on the outcomes of the event or problem, and in the case of unexpected serious adverse event or death, comment on the relationship to participation in the study. Based on the review of these events, the monitor should make a recommendation regarding study continuation. All decisions regarding study continuation, modification, or termination will be reported immediately or

annually, as appropriate, to the IRB, FDA, and other appropriate agencies. Reports for events determined by either the investigator or medical monitor to be possible or definitely related to study participation and reports of events resulting in death should be forwarded in compliance with current IRB policy and applicable federal regulations.

Adverse Event Reporting

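### Dose escalation is automatic on low AUC and few DLTs, and no number of grade 3 liver discontinuations can hold it back in the visible text

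*Combined protocol and SAP*

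**What the plan says.** The section on dose escalation criteria opens: "Dose escalation will take place if all the requirements listed below are met". Two requirements follow.

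- Item 1, on exposure: "The AUC/12 hours of the initial 2/3 patients is below 100 ng/ml".
- Item 2, on safety: "No more than 0 of 3 or 1/6 patients on the first dose level experience a dose limiting toxicity by day 30". A DLT is non-engraftment by day 30, a grade 4 liver event, or another grade 4-5 toxicity. The liver item reads "Grade 4 liver abnormalities, unless clearly related to stem cell transplant and not to the study drug".

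Grade 3 liver toxicity (ALT above 5 times or total bilirubin above 3 times the upper limit of normal) is handled elsewhere. The note to item 3 of the Stopping Rules says that it, "regardless of cause, will lead to permanent discontinuation of Maraviroc for that specific patient, but enrollment will continue". Discontinuation of therapy and Early termination of study drug repeat this and forbid re-challenge. The escalation criteria do not mention it.

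The Study design section says that a PK analysis after the first three patients decides between further observation and escalation, and it refers to Figure 1, which is not shown. Statistical analysis says that escalation continues "until a dose which yields 2 of 3 patients with AUC > 100ng/ml and no drug related toxicities". Under the Data Safety Monitoring Plan the medical monitor is to "review study data/progress a minimum of every 6 months", and more often at discretion.

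**The concern.** A rule that commits the study to a higher dose should be able to respond to the toxicity the protocol itself treats as most important. The protocol cites a boxed warning for hepatotoxicity, tests liver function every 48 hours on drug, and regards grade 3 liver toxicity as serious enough to end the drug for good. Because the drug stops at grade 3, some drug-related injury may never reach grade 4. That protects the child, but it weakens a count of grade 4 events as a guide to whether the next dose is safe. Much of the liver information then lies in the grade 3 discontinuations, and the escalation rule does not read them.

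At stake is a higher dose for children aged 2 to 12 in the first part of the study. The Abstract carries the dose established there into the second stage.

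**Working it through.** The plan states no figure on this point, so the main check is to run the rule as written.

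**1. The rule.** Take three children with AUC below target in at least two, and no non-engraftment or grade 4-5 toxicity. Vary only the number taken off drug for grade 3 liver toxicity.

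| Grade 3 liver discontinuations | Item 1 met | DLT count | Item 2 met | Result |
|---|---|---|---|---|
| 0 of 3 | yes | 0/3 | yes | escalate |
| 1 of 3 | yes | 0/3 | yes | escalate |
| 2 of 3 | yes | 0/3 | yes | escalate |
| 3 of 3 | yes | 0/3 | yes | escalate |

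**2. Text that might act as a brake.**

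- Statistical analysis, Phase I: freedom from drug-related toxicity describes the dose at which escalation ends. When AUC is low it does not forbid an increase.
- Data Safety Monitoring Plan: review is periodic, or prompted by unanticipated problems, unanticipated serious adverse events and deaths. It is not tied to escalation.
- Adverse Event Reporting: the investigator assesses each event, but no consequence for escalation is stated.
- Stopping Rules, item 3: the halt applies to grade 4 liver toxicity only.

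**3. Size of the step (Table 4).** 50/40 and 250/200 = +25%; 120/100 = +20%; 350/300 = +16.7%. One step is listed.

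**4. How often a loss might occur.** The documents give no rate for children after transplant. With rate p per child and independence, the chance of at least one loss in three is 1 − (1 − p)³.

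- p = 6% (grade 3/4 bilirubin, list of adverse effects in HIV populations): 1 − 0.94³ = 16.9%.
- Grade 3/4 transaminase rises are listed separately there at 2 to 5%, with overlap not given. With no overlap, p could reach 5 + 6 = 11%: 1 − 0.89³ = 29.5%.
- p = 2/13 = 15.4% (adult reduced-intensity transplant study, Previous Work): 1 − (11/13)³ = 39.4%. The exact 95% interval for 2/13 is 1.9 to 45.4%, which gives 5.6 to 84%.

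Loss of all three is rare: p³ = 0.02% at 6% and (2/13)³ = 0.36% at 2/13. That case shows the logic of the rule and is not a forecast.

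**5. Jointly with low exposure.** Let q be the chance that a child's AUC is below target. It is not given, so 10%, 30% and 50% are assumed. Item 1 is met with probability 3q²(1 − q) + q³ = 2.8%, 21.6% and 50.0%. Multiplying by the chance of at least one loss, under independence:

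| q | at p = 6% | at p = 2/13 |
|---|---|---|
| 10% | 0.5% | 1.1% |
| 30% | 3.7% | 8.5% |
| 50% | 8.5% | 19.7% |

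These are cohorts in which item 1 is met and at least one child has been lost; escalation is then required if item 2 is met too. If liver toxicity rises with exposure, the figures for low-AUC children would be lower. A child stopped before the second AUC may be replaced, so the joint figures are rough.

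**The case against.** The strongest reply is that the decision algorithm is in Figure 1, which cannot be seen, so a missing step cannot be asserted. This stands as a limit: the point covers the visible text only. The accompanying prose does describe that step as one of PK target attainment.

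Next, item 2 counts DLTs by day 30, so the liver results will be in hand before the dose rises, and one center with about three children will know which of them it took off drug. That is fair, and a careful team would look. But the rule as worded gives the team no ground for holding back after looking.

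Third, the risk is bounded. A child with grade 3 liver toxicity does not resume the drug, escalation happens only when exposure is low, and an unattributed grade 4 event halts the study. Grade 3 events of any cause include transplant injury. In the adult study, liver abnormalities did not recur on restarting. All of this stands and keeps the point minor.

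Three stronger readings are tempting, and the documents do not support them.

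- A reader might infer that grade 3 liver losses could go unrecorded, because laboratory values count as adverse events only under conditions. Adverse Event Reporting requires events of grade 3 and above to be recorded unless directly attributable to the underlying disease, and a value that ends treatment would ordinarily be judged clinically significant.
- A reader might infer that replacement hides these children from the DLT count, since those with an "incomplete course of study drug) will be replaced to achieve 12 dose verifications". That is a PK count. Item 2 counts patients on the first dose level, which includes any child dosed there.
- A reader might infer that the DLT definition is wrong to leave out grade 3. The split between stopping one patient and counting against the dose looks deliberate, and it is the sponsor's choice.

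**Conclusion.** The point holds and is minor. On the visible text, low AUC together with an acceptable DLT count compels an increase of 17 to 25%, and no number of permanent grade 3 liver discontinuations can prevent it. This follows from the wording and needs no assumption about rates, subject to Figure 1. The figures of about 17% and 39% only show that a loss among the first three children is plausible. They are borrowed from HIV populations and from adults after transplant, and not every event in those sources need be a drug effect. The documents do not support a claim that safety review is absent; what is absent is a link between that review and the escalation decision.

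**What to change.** In the dose escalation criteria, change *will* to *may* in the opening sentence and add a third requirement. Before any increase, the medical monitor reviews every grade 3 or higher liver discontinuation through day +30 at the current dose, with day of onset, days on drug and attribution, and agrees in writing that escalation is acceptable. State that the monitor may withhold agreement; a signature on a table without that power would leave the rule as it is.

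The DLT definition, its thresholds and the stopping rules do not change. The monitor is already in post, and the liver tests are already run every 48 hours. Item 3 of the Stopping Rules gives a precedent, since it requires the monitor's approval (with that of the IRB and FDA) to resume after an unattributed grade 4 liver event. The cost is a little protocol text, one documented review, and a short delay before escalation during which exposure stays below target.
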